4.6.1 Treatment

For each treatment, subjects will undergo bronchoscopy under general anesthesia or moderate sedation, at the discretion of the bronchoscopist. During both procedures, subjects will be treated with Coils according to the Instructions for Use. Subjects will receive prophylactic drugs pre-procedure and post-procedure.

Following LVRC placement (Visit 2), the subject will remain in the hospital under observation per standard hospital practice. Following hospital discharge, the subject will be contacted by phone one week after Visit 2 and will be seen at the study site at one month after Visit 2. After the one month visit following Visit 2, the subject will be scheduled for the second LVRC placement in the contralateral lung to take place approximately 2 months after Visit 2. Only a single lung will be treated during any bronchoscopy.

After the subject's second LVRC placement procedure (Visit 5), the subject will remain in the hospital under observation per standard hospital practice. Following hospital discharge, the subject will be contacted by phone one week after Visit 5 and will be seen for the tests, procedures and follow-up described in Table 6. Subjects will be followed up annually for 5 years. After the 5 year visit, the subject will exit the study.

Table 6. Visit Schedule

Procedure / Assessment	Visit 1 Pre-Treatment (Screening)	Visit 2 LVRC Placement #1	Visit 3 1 Week post Visit 2 ^a (Phone Call)	Visit 4 1 Month post Visit 2 ^b (Office Visit)	Visit 5 LVRC Placement#2 (2 Month post Visit 2)	Visit 6 1 Week post Visit 5 ^a (Phone Call)	Visit 7 1 Month post Visit 5 ^b (Office Visit)	Visit 8 6 Months post Visit 2 ^c (Office Visit)	Visit 9 9 Months post Visit 2 ^a (Phone Call)	Visit 10 12 Months post Visit 2 ^c (Office Visit)	Visit 11 24 Months post Visit 2 ^c (Office Visit)	Visit 12 36 Months post Visit 2 ^c (Office Visit)	Visit 13 48 Months post Visit 2 ^c (Office Visit)	Visit 14 60 Months post Visit 2 ^c (Office Visit)
Informed Consent	X													
Inclusion/ Exclusion	X													
Focused physical exam including vital Signs andSpO ₂	X	X		X	X		X	X		X	X	X	X	X
Record the following measures from the 12 Month RENEW Visit in the eCRF as baseline measurements: Spirometry, Lung Volumes and Diffusing Capacity, 6MWT, SGRQ, mMRC*		X												
Spirometry	X							X		X	X	X	X	X
Lung Volumes and Diffusing Capacity	X*							X		X	X	X	X	X
6MWT	X*			X			X	X		X	X	X	X	X
SGRQ	X*			X			X	X		X	X	X	X	X
mMRC	X*			X			X	X		X	X	X	X	X

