2.3.2.1 Event Time Periods

In order to assess the safety profile of the LVRC without the interference of the procedure effect, adverse events and major complications will be summarized by time period. Each event will be included in the time period in which the event began, with the periods defined as follows:

- Peri-procedural: 0-30 days post each of the two treatment visits (visit 2 or visit 5)
- Between treatment #1 and visit 5: More than 30 days after visit 2, but prior to visit 5
- Between treatment #2 (or treatment #1 for subjects that miss Visit 5) and 6 months: More than 30 days after visit 5, but prior to 6 months post treatment #1

- Between 6 and 12 months: 6 or more months post treatment #1 through visit 10

Regarding the programming specifications for inclusion of AE records through the 12-month visit and each follow-up time period, please refer to Appendix 4.1 (item F).

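### SAP 2.3.2.1: the first-year event periods overlap if the second treatment is about 3 months or more late, and no rule says which period prevails

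*SAP*

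**What the plan says.** SAP 2.3.2.1 gives the aim of the split: "In order to assess the safety profile of the LVRC without the interference of the procedure effect, adverse events and major complications will be summarized" in separate periods. The assignment rule is "Each event will be included in the time period in which the event began", which intends one period per event. The four bullets, numbered here in the order listed, are:

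1. "Peri-procedural: 0-30 days post each of the two treatment visits (visit 2 or visit 5").
2. "Between treatment #1 and visit 5: More than 30 days after visit 2, but prior to visit 5".
3. After treatment #2, or after treatment #1 for subjects who miss Visit 5: "More than 30 days after visit 5, but prior to 6 months post treatment #1".
4. "Between 6 and 12 months: 6 or more months post treatment #1 through visit 10".

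The section refers to Appendix 4.1 item F for inclusion of records, but item F covers only the 12-month and annual cut-offs. SAP 1.2.2 makes blocks of time within the 12 months part of the primary safety tabulation of major complications.

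On timing, Protocol 4.6.1 states that "the subject will be scheduled for the second LVRC placement in the contralateral lung to take place approximately 2 months after Visit 2". In Table 6 the follow-up contacts carry window footnotes a, b or c. Visit 5 carries none.

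**The concern.** Bullets 1 and 2 follow the actual date of Visit 5. Bullet 4 follows only the date of treatment #1. Bullet 3 joins the two systems, and it works only if days 0-30 after Visit 5 are over before month 6. When they are not, an event soon after the second bronchoscopy meets bullet 1 and bullet 4 together. If Visit 5 comes after month 6, an event between month 6 and Visit 5 meets bullets 2 and 4.

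At stake is the reading of the period tables. An event two days after a late second procedure would either be counted twice or be placed by a programmer's choice. One of the two possible places is a block intended to be largely free of the procedure effect. The study is descriptive (SAP 1.4), so these tables are themselves the result.

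There is a smaller gap of the same kind. For subjects who miss Visit 5, bullet 2 has no end date, yet bullet 3 already covers them from day 31 to month 6.

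**Working it through.** **Inputs**

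- Day 0 is treatment #1 (Visit 2). V is the day of Visit 5.
- M is the day on which 6 months is reached. The SAP gives no conversion. Protocol 2.4, Tables 1 to 4, uses 180 days; I assume a range of 180-184.
- Target V is 2 months, about day 61. Adding an assumed 4 weeks gives day 89.
- Days 0-30 after Visit 5 are 31 days: V to V + 30.

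The documents state no figure of their own to reproduce here.

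**Bullets 1 and 4.** They share days when V + 30 ≥ M. There is no overlap when V ≤ M − 31. The number of shared days is min(31, max(0, V + 31 − M)).

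**Bullets 2 and 4.** They share days only when V > M. The number is V − M.

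| M | Last V without overlap | 1 and 4 shared, V = 61 | V = 89 | V = 160 | V = 170 | V = 183 | V = 200 | 2 and 4 shared, V = 200 |
|---|---|---|---|---|---|---|---|---|
| 180 | 149 | 0 | 0 | 11 | 21 | 31 | 31 | 20 |
| 182 | 151 | 0 | 0 | 9 | 19 | 31 | 31 | 18 |
| 183 | 152 | 0 | 0 | 8 | 18 | 31 | 31 | 17 |
| 184 | 153 | 0 | 0 | 7 | 17 | 30 | 31 | 16 |

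Example with M = 183 and V = 170: the peri-procedural days are 170 to 200. Days 183 to 200 also meet bullet 4, and 170 + 31 − 183 = 18.

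**Delay needed.** 149 − 61 = 88 days and 153 − 61 = 92 days. Visit 5 must therefore be about 3 months beyond target before any day is shared.

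**Do the other visit windows rule this out?** They do not. The earliest Visit 7 is V + 30 − 14 (footnote b). The latest Visit 8 is M + 28 (footnote c). Keeping Visit 7 no later than Visit 8 requires V ≤ M + 28 − 16 = M + 12, which is day 192 for M = 180 and day 195 for M = 183. Both are past the last overlap-free day.

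**The case against.** The strongest reply is that the plan works as scheduled. Treatment #2 is set at about 2 months, day 150 is not about 2 months, and there is no overlap at day 61 or day 89. Deviations need the sponsor's prior approval except in an emergency (Protocol 12), and they are tabulated (SAP 2.6). This stands as a limit on reach.

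The singular wording of the assignment rule, the listing of the peri-procedural bullet at the head, and the stated aim all point to peri-procedural precedence as the natural reading. That is fair, and it means the SAP does not itself call for double counting. But precedence is not written down, and bullet 4 as worded includes the procedural days.

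The missing window for Visit 5 carries limited weight. Neither placement visit has one, and a tolerance may exist in the Study Operational Instructions, which are not among these documents.

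Mitigation is real. SAP 2.3.2.3 summarises device- or procedure-related events separately and lists onset in days relative to the procedure. An affected event stays identifiable, although the period tables are not corrected.

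A reader might go further and infer that delay is common, or that it is concentrated in subjects with a complicated first procedure, from the 17.2% and 5.9% serious-event rates in Protocol Table 5. The documents do not support that. Those are per-procedure rates up to 6 months, they do not separate first from second procedures, and they say nothing about delay.

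**Conclusion.** The rule in SAP 2.3.2.1 is faulty as stated, but only for late second treatments. Its periods are mutually exclusive only if Visit 5 is on or before about day 149-153, assuming 6 months is 180-184 days. Beyond that, between 1 and 31 peri-procedural days also meet the 6-12 month period. If Visit 5 is after month 6, the days from month 6 to Visit 5 meet bullets 2 and 4 as well.

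Two stronger readings should be resisted. One is that procedural events will in fact be counted as 6-12 month events. No Visit 5 dates are given, so the number affected is unknown and may be small or zero. The other is that the primary safety result is wrong. The count of subjects with at least one major complication within 12 months does not depend on these boundaries; only the breakdown by block does. Bullet 4 is also named by time alone, so calling its contents device events would go beyond the SAP.

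The point is worth settling before tabulation because the tables at risk are the ones meant to show safety apart from the procedure.

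**What to change.** Change SAP 2.3.2.1 only:

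- State that the peri-procedural period takes precedence over all other periods.
- In bullet 4, add the exclusion of days 0-30 after Visit 5.
- For subjects who have a Visit 5, end bullet 2 at the earlier of Visit 5 and 6 months post treatment #1. Non-procedural events from month 6 onward then go to bullet 4.
- State that bullet 2 does not apply to subjects who miss Visit 5. Their events from day 31 to month 6 stay in bullet 3.

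The last item is needed because capping bullet 2 at 6 months for everyone would give subjects without a Visit 5 an interval that bullet 3 already assigns to them.

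Check with M = 183 and V = 200: bullet 1 holds days 0-30 and 200-230, bullet 2 holds days 31-182, bullet 3 is empty, and bullet 4 holds days 183-199 and from 231 to Visit 10. Each day falls in one period. With no Visit 5, bullet 1 holds days 0-30, bullet 3 days 31-182, and bullet 4 the rest.

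The cost is one extra programming condition and no new data. Whether Visit 5 should carry a window in Table 6 is for the sponsor to reconcile. This fix does not depend on it.

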2.3.2.3 Adverse Events

MedDRA system organ classes and preferred terms will be summarized for all AEs. Summaries will include event and subject counts. For the events summarized by subject counts, each subject will be counted only once within a system organ class or a preferred term by using the adverse events with the highest severity within each category.

SAE, AEs, and AEs related to device or procedure will be summarized separately. Additionally, summaries for major complications will also be included. A high level summary for SAEs and AEs will also be provided. All summaries will be presented by each follow up time period. Similarly, device or procedure related SAEs and non-SAEs will be presented by severity.

In addition, all information pertaining to AEs noted during the study will also be listed by subject. Details of the line listing by subject will include verbatim term given by the Investigator, preferred term, system organ class, start date, stop date, severity, and device or procedure relatedness. The AE onset will also be shown relative (in number of days) to the day of the procedure.

2.4 Subgroup Analysis

The following subgroup analyses will be presented for effectiveness and safety endpoints.

- US vs. OUS (outside of the US)
- Heterogeneity of emphysema
- Severity of air trapping (RV >225% vs. RV < 225%)

2.5 Interim Analysis

The efficacy and safety analyses as described herein will occur following the completion of the 12-month follow-up visit for all patients per the protocol defined endpoints. Additionally, the analyses will be performed at 24 month follow-up, 36 month follow-up, 48 month follow-up and 60 month follow-up.

There are no formal additional interim analyses planned for this study.

2.6 Protocol Deviations

The frequency of protocol deviations (PD) will be summarized by major and minor as defined in the study protocol deviation plan, by center, by category and by category within major and minor by each time period.

2.7 Additional Descriptive Analysis

Additional descriptive summary statistics will be presented for clinical assessments (such as plethysmography and spirometry measures), procedural and device data, and efficacy results.

For continuous variables, summary statistics (sample size (N), mean, standard deviation (STD), median, minimum, and maximum).

For categorical variables, results will be summarized with frequency distributions by follow-up time period.

2.8 Documentation and Other Considerations

All analyses will be performed using SAS® for Windows, version 9.3 or above.

4. APPENDIX

4.1 Programming Specifications

A. Required margins: at least 1.25 inches on the binding margin and at least 1 inch on all other sides. All output should have the following header at the upper left margin:

PneumRx - BTG International
Protocol: CLN0016.p. D

and the following header (right-justified) at the upper right margin:

Page n of N
DDMMYY

Tables/appendices/listings should be internally paginated (i.e., page numbers should appear sequentially within each table).

All output should have SAS program name in the lower right and the data source(s) used to generate the output in the lower left:

Data
Source: xxx PROGRAM: XYZ.sas

B. In general, data listings should be sorted by subject number and visit/start dates, unless specific instructions to do otherwise.

C. The following algorithm should be used to impute adverse event start dates for which only partial information is known:

- Missing day and month
 - If the year is same as the year of treatment (LVRC), then the day and month of treatment (LVRC) is assigned to the missing fields.
 - If the year is prior to or after the year of treatment, then January 1 is assigned to the missing fields.
- Missing month only
 - Treat day as missing and replace both month and day according to the above procedure.
- Missing day only
 - Then the first day of the month is assigned to the missing day.

If the AE date of resolution is complete and the imputed start date as above is after the resolution date, the start date is imputed using the resolution date.

Adverse events with partially missing stop dates are imputed a resolution date as follows:

- *year is missing* – the date is left missing.
- *month is missing* – impute “December.”

- *day is missing* – impute last date of that month.

D. Complete dates for concomitant medications (CM) with missing or partially missing start dates are imputed using the same algorithm described for adverse event onset dates. If the end date is missing or partially missing, the imputation rule is applied in the following order:

- 1) *year is missing* – the medication is considered to have been received at all periods after the period determined by the start date. The date is left missing.
- 2) *month is missing* – impute “December.”
- 3) *day is missing* – impute last date of that month.

E. Date imputations are applied to the process of assigning treatment period and study day and should be retained in the derived database, but the data listings should display the original, partially missing dates.

F. Specifications regarding the inclusion of AE/CM/PD records

- 1) up to 12-month visit are defined as follows:
 - Completed 12 month visit – then include all records with AE/CM/PD onset dates \leq the actual 12 month visit date.
 - Missing 12 month visit – then include all records with AE/CM/PD onset dates \leq 13 months post treatment #1 date.
- 2) 12 – 24 month are defined as follows:
 - Completed 24 month visit – then include all records with AE/CM/PD onset dates \leq the actual 24 month visit date and \geq actual 12 month visit date.
 - Missing 24 month visit – then include all records with AE/CM/PD onset dates \leq 25 months post treatment #1 date and \geq actual 12 month visit date.
- 3) 24 – 36 month are defined as follows:
 - Completed 36 month visit – then include all records with AE/CM/PD onset dates \leq the actual 36 month visit date and \geq actual 24 month visit date.
 - Missing 36 month visit – then include all records with AE/CM/PD onset dates \leq 37 months post treatment #1 date and \geq actual 24 month visit date.
- 4) 36 – 48 month are defined as follows:
 - Completed 48 month visit – then include all records with AE/CM/PD onset dates \leq the actual 48 month visit date and \geq actual 36 month visit date.
 - Missing 48 month visit – then include all records with AE/CM/PD onset dates \leq 49 months post treatment #1 date and \geq actual 36 month visit date.
- 5) 48 – 60 month are defined as follows:
 - Completed 60 month visit – then include all records with AE/CM/PD onset dates \leq the actual 60 month visit date and \geq actual 48 month visit date.
 - Missing 60 month visit – then include all records with AE/CM/PD onset dates \leq 61 months post treatment #1 date and \geq actual 48 month visit date.

G. Unless otherwise noted, the mean (standard deviation) of a set of values should be printed out to one (two) more decimal(s) than the raw value.

e.g., raw: xx
 mean and standard deviation: xx.x and xx.xx
 range (minimum and maximum): xx, xx

- H. All table percentages should be reported with one decimal point unless otherwise noted.
- I. Missing data should be represented on patient listings as 1) dashes “-,” and properly footnoted: “- = data not available” or 2) “n/a,” with footnote “n/a = not applicable,” whichever is appropriate.
- J. Times should be printed in the format “HH:MM.” “HH” represents the 2-digit hour portion of the time. “MM” represents the 2-digit minute portion of the time. Both hour and minute portions of time are zero-filled on the left if they have only one digit. Missing time portions should be represented on patient listings as dashes (“10:--” and “--:--”). Times that are missing because they are not applicable for the patient should be printed as “n/a,” unless otherwise specified.

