4.5 Safety Evaluation

Safety will be evaluated by collection of AEs and SAEs from entry into the study (Visit 1) until Visit 10 (12 months Follow-up from Visit 2) or until the subject has completed or terminated from the study.

Prior to discharge after treatments and at each phone call or follow-up visit, subjects will be instructed to report to the investigator any adverse physical or mental changes they experienced since the previous visit/interview. All such AEs/SAEs reported by the subjects or observed by the investigators will be recorded.

Safety data from the various OUS studies that PneumRx has conducted to date have been collected and analyzed. A summary of the safety data is provided in Section 2.4, above.

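### An AE with only its onset day missing is dated to the 1st even in the month of treatment #1, so a post-procedure event can be dated before treatment and fit none of the four event time periods

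*SAP*

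**What the plan says.** SAP Appendix 4.1 item C sets out how partial AE onset dates are completed.

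- **Day only missing:** "Then the first day of the month is assigned to the missing day". There is no check against a treatment date.
- **Day and month missing, year equal to the treatment year:** "then the day and month of treatment (LVRC) is assigned to the missing fields". The text does not say which of the two treatments is meant.
- **Override:** if the AE has a complete resolution date and the imputed start falls after it, "the start date is imputed using the resolution date". This can only move a start earlier.
- **Partial stop dates:** a missing day leads to "impute last date of that month", and a missing month to December.

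Item D extends the onset rule to concomitant medications, whose start dates "are imputed using the same algorithm described for adverse event onset dates". Item E says "Date imputations are applied to the process of assigning treatment period and study day", while listings keep the original partial date.

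SAP 2.3.2.1 assigns each event to the period in which it began. The earliest of its four periods starts at day 0 of treatment #1, and no row covers earlier onset. For inclusion through the 12-month visit it points to item F(1), which says "then include all records with AE/CM/PD onset dates" up to that visit (or up to 13 months after treatment #1 if the visit is missing) and sets no lower limit. SAP 2.3.2 summarizes treatment-emergent AEs without defining them. Protocol 4.5 collects AEs from Visit 1, so genuine pre-treatment events also exist.

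**The concern.** The period tables are meant to separate the effect of the procedure from that of the implanted coil. The day-only rule fails at the boundary where that separation starts: it can date an event before the procedure that it followed.

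The rules also run in the wrong order of precision. An event recorded only by year, in the treatment year, is placed on the treatment date and counted as peri-procedural. The same event recorded by month and year is placed before treatment and counted in no period. That is hard to read as deliberate.

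Results are descriptive (SAP 1.4), so the tabulated counts are the output, and nothing in the tables would show that events had been re-dated. Because treatment-emergent is undefined, two programmers could reasonably keep or drop the same event.

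**Working it through.** The plan gives no figure to reproduce here, so the rule was applied to calendar dates.

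**Worked example** (treatment #1 on 15 June 2015, Visit 5 on 14 August 2015)

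| True onset | Recorded as | Imputed | Days from treatment #1 | Period in 2.3.2.1 |
|---|---|---|---|---|
| 20 June | June 2015 | 1 June | -14 | none (truly peri-procedural) |
| 20 June | 2015 | 15 June | 0 | peri-procedural |
| 10 July | July 2015 | 1 July | 16 | peri-procedural |
| 20 August | August 2015 | 1 August | 47 | between treatment #1 and Visit 5 (truly peri-procedural) |

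The first row still satisfies item F(1), since 1 June 2015 is before the 12-month visit.

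**Share dated before treatment #1.** Assumptions: treatment #1 equally likely on each of the 1,096 days of 2014-2016; true onset on day 0-30; only the day missing.

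*Flat onset.* In a month of m days with treatment on day k (k ≥ 2), the m - k + 1 days from k to month end are all imputed to the 1st, before treatment. Summing over k gives m(m - 1)/2 per month.

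- 21 months of 31 days: 21 × 465 = 9,765
- 12 months of 30 days: 12 × 435 = 5,220
- February, 28 + 29 + 28 days: 378 + 406 + 378 = 1,162
- Total 16,147 out of 1,096 × 31 = 33,976, or 47.5%

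*Front-loaded onset.* Weighting day l by exp(-l/mean) in the same enumeration gives 56.1% for a mean of 30 days and 76.6% for a mean of 7 days.

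**Illustrative size.** If 2-10% of AEs lacked only the day (an assumption), the share of day 0-30 AEs after treatment #1 dated before it would be 0.475 × 2% to 0.475 × 10% = 1.0-4.8% (flat), or 0.766 × 2% to 0.766 × 10% = 1.5-7.7% (mean 7 days).

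**Net effect on the peri-procedural count.** Both windows together, treatment #2 at +61 days, as a share of the true missing-day count. *In* means events from later days pulled back into a window.

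| Onset | Out to pre-treatment | Out to the between row | In | Net |
|---|---|---|---|---|
| Flat | 24% | 24% | 48% | 0% |
| Mean 7 days | 38% | 38% | 1% | -76% |

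**With a floor at treatment #1.** The pre-treatment outflow disappears, but true pre-treatment events in that month come in. Let r be the daily AE rate before treatment divided by the mean daily rate in days 0-30. Summing the k - 1 earlier days of the month again gives m(m - 1)/2, so with at least a month of screening the inflow is 0.475r of the treatment #1 window, or 0.238r of both windows.

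- Flat, net: 0.475 - 0.238 + 0.238r, which is +24% at r = 0 and +48% at r = 1.
- Mean 7 days, net: 0.009 - 0.383 + 0.238r, which is -37% at r = 0 and -14% at r = 1.
- Errors across the treatment #1 line: the floor makes fewer than the present rule when r is below 0.475/0.475 = 1.00 (flat), 0.561/0.475 = 1.18 (mean 30) or 0.766/0.475 = 1.61 (mean 7).

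**The case against.** A reader might infer that these events vanish from all reporting. The documents do not support that. Item F(1) has no lower bound, so the event meets the up-to-12-month window. It leaves the overall summary only if treatment-emergent is read as onset on or after treatment #1, which the SAP does not say.

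A reader might also infer that the primary safety result is biased. SAP 1.2.2 counts subjects with a major complication within 12 months post-baseline, and SAP 2.2 puts baseline at the last assessment before treatment. An event re-dated to the 1st can therefore still be post-baseline. Major complications also mostly involve hospital care with a known date.

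A third inference, that the peri-procedural count is understated, needs front-loaded onset, on which the documents give no data. Under flat onset the present rule's net error is zero, and the floor adds events.

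The upper end of the illustrative range is probably pessimistic. With a mean of 7 days, 69% of day 0-30 onsets fall by day 7, around the hospital stay and the one-week call, when dates are least likely to be incomplete.

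All of this stands and limits the size of the problem. It does not remove it: the rule can still date a post-procedure event before the procedure, and it conflicts with the SAP's own year-only rule.

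**Conclusion.** The defect is real and visible in the SAP text. Item C, through item E, can give a post-procedure AE a pre-treatment date, a negative study day and no row in 2.3.2.1. About 48% to 77% of day 0-30 events after treatment #1 with only the day missing would be affected, depending on the onset pattern; these shares assume that missingness is unrelated to onset timing. The number of events cannot be determined, because the documents give no partial-date rate. It is probably small and mostly non-serious.

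At treatment #2 the same rule only moves events between two rows, and any alternative there trades one misclassification for another.

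This is worth correcting because the rule is wrong as written and cheap to repair. It does not threaten the study's overall conclusions.

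**What to change.** Amend the SAP as follows.

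- **Item C, AE onset, day only missing:** if the month and year are those of treatment #1, impute the treatment #1 date; otherwise impute the 1st. Then apply the existing resolution-date override, so that an event with a complete stop date before treatment #1 stays pre-treatment.
- **Year-only rule:** state that the treatment meant is treatment #1. Year-only dates should not be anchored to treatment #2: that would put every such event at its day 0 whenever the two procedures straddle a year end (61/365 = 17% of start dates at a 61-day gap).
- **Treatment-emergent:** define as onset on or after treatment #1.
- **Item D:** state that the floor does not apply to concomitant medications.
- **Period tables:** footnote the number of events whose onset day was imputed.

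A sensitivity table with the floor also applied at treatment #2 is optional. It should not be the main rule: under flat onset with r = 1, inflow to the two windows would reach about 95% of the true missing-day count, and the between row would fall.

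The work is a handful of sentences, a few lines of code and the footnotes. The statistical cost is that some AEs that truly began before treatment #1 in that month become day-0 events. Under flat onset with r = 1 this is up to 24% of the true missing-day count of both windows with at least a month of screening, or 17% with 14 days (screening length is an assumption). At an assumed 10% missing rate that is at most 0.238 × 10% = 2.4% of peri-procedural AEs. The floor can therefore overstate the peri-procedural count if onset is flat, and should not be described as simply conservative.

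### After month 12, the annual safety windows in SAP Appendix 4.1 item F share the visit day and have no start date after a missed visit, so records can be counted twice or lost

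*SAP*

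**What the plan says.** SAP section 2.3.2.1 gives the principle for the periods up to Visit 10: "Each event will be included in the time period in which the event began". For the 12-month cut and the later periods it sends the programmer to the appendix, on "inclusion of AE records through the 12-month visit and each follow-up time period, please refer to Appendix 4.1 (item F").

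Item F of SAP section 4.1 sets the first window by an upper limit only:
- 12-month visit done: "Completed 12 month visit – then include all records with AE/CM/PD onset dates \leq the actual 12 month visit date".
- 12-month visit missed: "Missing 12 month visit – then include all records with AE/CM/PD onset dates \leq 13 months post treatment #1 date".

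The 12–24 month window has two limits:
- 24-month visit done: onset on or before "the actual 24 month visit date and \geq actual 12 month visit date".
- 24-month visit missed: onset on or before "25 months post treatment #1 date and \geq actual 12 month visit date".

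The 24–36, 36–48 and 48–60 month windows follow the same pattern, with missed-visit ends at 37, 49 and 61 months after treatment #1.

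These windows feed the safety tables. SAP 2.3.2.3 states: "All summaries will be presented by each follow up time period". SAP 2.6 tabulates protocol deviations "by category and by category within major and minor by each time period".

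**The concern.** There are two faults, and the second is the larger.

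1. **Shared day.** Each window includes its closing visit date, and the next window includes the same date as its opening day. An onset on the 12-, 24-, 36- or 48-month visit day meets the rule for both periods. Findings made at a visit may well carry that date.

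2. **Undefined start.** Item F foresees a missed visit and supplies a substitute end for that visit's own window. It supplies no substitute start for the window that follows, which still refers to an actual visit date that never occurred. Items C to E deal with partial event and medication dates, not absent visit dates.

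The study tests no hypothesis (SAP 1.4), so the descriptive tables are its result. Two programmers who follow the text faithfully could report different adverse event, serious adverse event, major complication, medication and deviation counts for 12–24 through 48–60 months. One version drops events from the period tables. The other shows first-year events, including peri-procedural ones, as late events, which works against the separation of procedure effects by timing that SAP 2.3.2 asks for.

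**Working it through.** The plan states no figure on this point, so the check applies item F as written to every possible onset day.

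**Inputs**
- From item F: the inclusive limits at both ends, and missed-visit ends at 13, 25, 37, 49 and 61 months after treatment #1.
- Assumed: visits on days 365, 731, 1096, 1461 and 1826 after treatment #1, and 1 month = 365.25/12 = 30.4375 days. The missed-visit ends are then days 396, 761, 1126, 1491 and 1857.
- Item F does not say how to evaluate onset ≥ a visit date that does not exist. Both codings were run: the condition fails (record excluded) or it is met (no lower limit).

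**All visits attended.** Days 365, 731, 1096 and 1461 each lie in two windows: 4 double-counted days, none lost.

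**One visit missed**

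| Missed visit | If the condition fails: days in no window | If the condition is met: days in two or more windows |
|---|---|---|
| 12 months | 397–730: 730 − 396 = 334 | 0–396 (397 days) + 3 shared visit days = 400 |
| 24 months | 762–1095: 1095 − 761 = 334 | 0–761 (762 days) + 2 shared visit days = 764 |
| 36 months | 1127–1460: 1460 − 1126 = 334 | 0–1126 (1,127 days) + 1 shared visit day = 1,128 |
| 48 months | 1492–1826: 1826 − 1491 = 335 | 0–1491 = 1,492 |

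If the 12- and 24-month visits are both missed and the condition fails, days 397–1095 are lost: 1095 − 396 = 699.

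**Example.** A subject misses only the 12-month visit and has adverse events on days 10, 200 and 500. By onset, one of them (day 500) belongs to 12–24 months. If the condition fails, that period shows 0 events and the day-500 event is in no period. If it is met, the period shows 3, two of which are also in the first window.

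**All attendance patterns.** There are 2^5 = 32 patterns of attended and missed visits from 12 to 60 months. Onset days from 0 to the end of the last window were counted.

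| Rule | Lost days (range) | Double-counted days (range) | Patterns with any error |
|---|---|---|---|
| As written, condition fails | 0 to 1,461 | 0 to 4 | 32 of 32 |
| As written, condition met | 0 | 4 to 1,492 | 32 of 32 |
| Start strictly after the previous end | 0 | 0 | 0 of 32 |

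**Sensitivity.** The visit schedule allows ±4 weeks, so the 24-month visit can fall on days 703 to 759. With the 12-month visit missed, the lost span then runs from 702 − 396 = 306 to 758 − 396 = 362 days. Placing the nominal 24-month visit on day 730 instead of 731 gives 333.

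**The case against.** The strongest reply is that no sensible programmer would adopt either extreme. SAP 2.3.2 says the summaries cover all events in each follow-up period, which argues against losing a day-500 event. The label of the 12–24 month window argues against putting a day-10 event in it. On that view the real doubt is only whether the period starts at 12 or 13 months, about 30 days. This shows what was intended, but item F is the rule that will be programmed and it does not state that intention. A choice between 12 and 13 months would still be an unspecified one.

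Several narrower points stand as limits:
- The one-period sentence in SAP 2.3.2.1 is written for periods up to Visit 10. The missing start date is a defect without it.
- With full attendance the fault is only 4 shared days. The 32-of-32 result shows that the rule is never clean, not that the error is always large.
- Many missed visits will follow death or withdrawal, and the lost days then hold no records.
- All adverse events are listed by subject with onset relative to the procedure (SAP 2.3.2.3), so none leaves the report and period counts could be rebuilt.
- Item D treats medications with a missing end year as continuing into later periods. That concerns ongoing use, whereas item F works on onset dates.
- Enrolled but untreated subjects have no treatment #1 date for the cut-offs. This limit is already in item F, and the change proposed here neither creates nor removes it.

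**Conclusion.** The concern holds. As written, item F does not give each record one period after month 12. The shared visit day is a small fault. The undefined start matters more: one missed annual visit in a subject who stays in follow-up puts about 11 months of onsets at risk of being lost (334 or 335 days on nominal visit dates; 306 to 362 for a missed 12-month visit within the allowed window for the 24-month visit), or lets all earlier history be counted again.

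The lost and recounted spans depend on the assumed visit days and on how a program handles the missing date. The existence of the fault does not. The documents give neither adverse event nor missed-visit rates for this study, so the number of records affected is unknown. The up-to-12-month counts, and so the primary tabulation of major complications, are unchanged. The point should be fixed before the 24-month and later tables are programmed.

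**What to change.** In SAP Appendix 4.1 item F, leave the first window as it is and redefine the four later ones: a record belongs to a window if its onset is strictly after the end of the previous window and on or before the end of the current one. Define the end of a window once, as the actual visit date if the visit took place, and otherwise the existing cut-off of 13, 25, 37, 49 or 61 months after treatment #1. An onset on a visit day then belongs to the period that the visit closes, and a missed visit leaves neither a gap nor an overlap.

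The cost is four changed lower bounds in the appendix and the matching program lines. No new data are needed.
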